	• Using the Kaplan-Meier method, estimate its associated statistics on TTP (including the median TTP with two-sided 95% CI, the TTP rates at clinically meaningful timepoints with two-sided 95% CI) for all participants who received at least one dose of lorlatinib without regard to discontinuation from treatment unless death occurs, new anti-cancer therapy is initiated or extended gap in tumor assessment is present prior to progression. TTP is defined as the time from date of first dose to the date of the first documented PD.				
	This analysis is based on ITT population. Participants with an event more than 12 weeks (24 weeks post the first 42 weeks) after the last adequate tumor assessment will be censored on the date of the last adequate tumor assessment prior to the gap that documented no progression. If the participant dies before progression, the participant will be censored on the date of death. If a new anticancer therapy starts prior to an event, the participant will be censored on the date of the last adequate tumor assessment that				

Endpoint	Statistical Analysis Methods				
	documented no progression prior to start of the new anti-cancer therapy. Participants with inadequate baseline assessment or with a adequate post-baseline tumor assessments within 12 weeks after the start date will be censored on the start date, unless the participant dies within 12 weeks of the start date, in which case, the patient who be censored on date of death. The CI for the median TTP will be calculated according to Brookmeyer and Crowley method, and the CIs for the survival function estimates at the timepoints will be derived using the log(-log) method.				
	PFS by ICR/INV				
	• Using the Kaplan-Meier method, estimate its associated statistics of PFS (including the median PFS with two-sided 95% CI, the PFS rates at clinically meaningful timepoints with two-sided 95% CI) for all participants who received at least one dose of lorlatinib without regard to discontinuation from treatment unless new anti-cancer therapy is initiated or an extended gap in tumor assessment is present prior to progression or death. PFS is defined as the time from date of first dose to the date of the first documented PD or death due to any cause, whichever occurs first.				

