6.2.8. TTP by ICR/INV

Analysis set: ITT: All enrolled participants who take at least 1 dose of Lorlatinib

Analysis methodology:

TTP is defined as the time from date of first dose to the date of the first documentation of PD per RECIST v1.1 as assessed by ICR/INV and will be summarized in months:

TTP (months) = [date of PD or censoring–date of treatment start +1]/30.4375.

TTP data will be censored as follows:

- For participants who start a new anti-cancer therapy prior to an event, censoring will be at the last adequate tumor assessment (see Section 5.2.9) prior to the start of new anti-cancer therapy. Note: if date of progression occurs on the same date as the start of new anti-cancer therapy, the progression will be counted as an event.
- For participants with documented progression or death after two or more missing tumor assessments, censoring will occur at the last adequate tumor assessment prior to the missing assessments. In this study antitumor activity will be assessed through radiological tumor assessments conducted at screening and every 6 weeks until disease progression regardless of initiation of subsequent anti-cancer therapy. The allowable time window for disease assessments is ±1week while on treatment and whenever disease progression is suspected (eg, symptomatic deterioration). Therefore time without adequate assessment is defined as 98 days (12 weeks plus 2 weeks).
- For participants who do not have an adequate baseline tumor assessment or who do not have any post-baseline tumor assessments, censoring will occur on the date of first dose unless death occurred on or before the time of the second planned tumor assessment (ie, on or before day 98) in which case the death will be considered an event. Note for participants who died without any post baseline assessments and meet the definition of

DMB02-GSOP-RF02 4.0 Statistical Analysis Plan Template 01-Nov-2018 PFIZER CONFIDENTIAL Page 30 TMF Doc ID: 98.03 two or more missing assessment the reason for censoring will be documented as two or more missed assessments and censoring will occur on the date of first dose.

• All other participants alive without objective progression will be censored on the date of the last adequate tumor assessment.

The date of tumor response at each nominal timepoint based on the ICR/INV assessments will be used for determining the dates of last adequate assessment for censoring purposes.

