The censoring and event date options to be considered for the TTP analysis are presented in Table 4.

Scenario	Date of event/censoring	Outcome
No adequate baseline assessment	date of first dose	Censored
Progression \leq 98 days after last adequate tumor assessment or \leq 98 days after date of first dose	Date of progression	Event
Death \leq 98 days after last adequate tumor assessment or \leq 98 days after date of first dose	Date of death	Censored
Progression or death > 98 days after the last adequate tumor assessment ^a	Date of last adequate assessment ^b documenting no	Censored
No progression	PD prior to anti-cancer therapy or missed assessments	
New anti-cancer therapy given prior to PD	therapy of missed assessments	

 Table 4.
 Outcome and event dates for TTP analyses

^a if there are no adequate post-baseline assessments prior to PD or death, then the time without adequate assessment should be measured from the date of first dose; if the criteria were met the censoring will be on the start date.

Summaries used for reporting:

Kaplan-Meier estimates (product-limit estimates) will be presented together with a summary of associated statistics including the median TTP time with two-sided 95% CIs. The TTP rate at 12 months will be estimated with corresponding two-sided 95% CIs. The CIs for the median will be calculated according to Brookmeyer and Crowley and the CIs for the survival function estimates at the timepoints defined above will be derived using the log(-log) method according to Kalbfleisch and Prentice (conftype=loglog default option in SAS Proc LIFETEST). The estimate of the standard error will be computed using Greenwood's formula.

Frequency (number and percentage) of participants with PD and each censoring reasons will be presented along with the overall event and censor rates.

Reasons for censoring will be summarized according to the categories in Table 5. If a participant meets multiple definitions for censoring the list will be used to define the hierarchy.

Hierarchy	Condition	Censoring Reason
1	No adequate baseline assessment	No adequate baseline assessment
2	Start of new anti-cancer therapy before event.	Start of new anti-cancer therapy
3	Event more than 98 days from last adequate post-baseline tumor assessment/start date	Event after missing assessments ^a
4	No event and withdrawal of consent date ≥ start date OR End of study (EOS) = Subject refused further follow-up	Withdrawal of consent

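### For a death without documented progression after a long scan gap, Protocol 9.4.1 read literally censors TTP at the date of death, while SAP 6.2.8 censors it at the last adequate scan

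*Protocol*

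**What the plan says.** Protocol 9.4.1 defines the endpoint by progression alone: "TTP is defined as the time from date of first dose to the date of the first documented PD". Three censoring rules follow.

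- Gap rule: "Participants with an event more than 12 weeks (24 weeks post the first 42 weeks) after the last adequate tumor assessment will be censored", with censoring at the last scan before the gap.
- Death rule: "If the participant dies before progression, the participant will be censored on the date of death".
- Start-date rule, for an inadequate baseline or no adequate scan in the first 12 weeks after the "start date will be censored on the start date, unless the participant dies within 12 weeks of the start date"; an early death of that kind is censored at the death date.

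SAP 6.2.8 has a gap rule that names death: "For participants with documented progression or death after two or more missing tumor assessments, censoring will occur at the last adequate tumor assessment". It sets the gap at 98 days. In SAP Table 4, a death within 98 days of the last adequate scan (or of first dose) is censored at the date of death. The next row, "Progression or death > 98 days after the last adequate tumor assessment", is censored at that assessment, or at the start date if there was none.

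**The concern.** Only progression is a TTP event in the protocol, so a gap rule written for participants with an event does not, read literally, reach a death without progression. The death rule then applies however old the last scan is. A progression found after a long gap is pulled back to the last scan because disease status in between was unknown. A death after the same gap leaves the participant in the risk set as progression-free until death. In advanced lung cancer, progression may well have occurred unseen in that interval.

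Two things are at stake: TTP would be flattered in lorlatinib's favour, and the two governing documents would give different TTP times for the same participant.

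**Working it through.** **1. Gap lengths.** Scans are every 6 weeks ±1 week (Protocol 8.1.1). The SAP's figure reproduces: 2 × 6 + 2 × 1 = 14 weeks; 14 × 7 = 98 days. The protocol's limits are 12 × 7 = 84 days, and 24 × 7 = 168 days after week 42 (day 294).

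**2. The rules side by side.** Days are counted from first dose, with an adequate baseline and no documented progression. The third protocol column assumes that *event* includes death and that the gap rule then prevails.

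| Last adequate scan | Death | Gap (days) | Protocol, literal | Protocol, *event* includes death | SAP Table 4 |
|---|---|---|---|---|---|
| 84 | 264 | 180 | 264 | 84 | 84 |
| 84 | 170 | 86 | 170 | 84 | 170 |
| 336 | 450 | 114 | 450 | 450 | 336 |
| none | 77 (week 11) | 77 | 77 | 77 | 77 |
| none | 90 | 90 | start | start | 90 |
| none | 150 | 150 | start | start | start |

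In row 1 the literal protocol and the SAP differ by 180 days: 180/30.4375 = 5.9 months. Row 3 differs by 114 days (3.7 months) under either reading of the protocol. Row 2 differs from the SAP only on the wider reading. Row 5 differs in the opposite direction: the SAP gives the longer time.

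**3. Direction of the effect in rows 1 and 3.** The Kaplan-Meier estimate is S(t) = ∏(1 − dᵢ/nᵢ). Moving a censoring date from the last scan to the later death adds that participant to nᵢ at each progression time in between and leaves dᵢ unchanged. No factor can fall, so S(t) rises or stays the same.

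**4. Size, on the literal reading.** The number of such deaths, k, and the TTP distribution are not in the documents, so these are assumptions: N = 70; 70 − k participants with exponential TTP, median 7 months, and administrative censoring uniform over months 12 to 24; k deaths without progression, last scan at month 3, death at month 7 or 10. The gaps are 4 × 30.4375 = 122 days and 7 × 30.4375 = 213 days, both over 98. There were 1,500 replicates per setting.

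Rise in the 12-month progression-free estimate when censoring is at death instead of the last scan, in percentage points:

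| k | Death at month 7 | Death at month 10 |
|---|---|---|
| 1 | 0.3 | 0.6 |
| 2 | 0.6 | 1.2 |
| 4 | 1.1 | 2.3 |
| 6 | 1.7 | 3.5 |
| 8 | 2.3 | 4.7 |

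The median does not move at k = 1 or 2. At k = 6 with death at month 10 it goes from about 7.4 to 7.9 months. A second set of assumptions (median about 6 or 12 months, 1 to 7 such deaths, gaps of 120 to 300 days) gives 0.2 to 4.9 points and 0.01 to 1.1 months.

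If *event* includes death and the gap rule prevails, the patterns in the table above give no difference, because the last scan falls before week 42 and both documents go back to it.

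**The case against.** **The SAP governs.** Protocol section 9 and SAP section 2 let the SAP modify the protocol, and promise an amendment only for major changes to the primary endpoint. The SAP rule is clear, so one could simply apply it. But the SAP's version history ties it to a protocol of 31 July 2019, the protocol supplied is dated 22 January 2020, and the SAP does not flag this rule as a departure. It cannot be read as a deliberate override of the later text.

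***Event* was meant to include death.** The SAP's gap rule names both, and the TTP estimand in Protocol 9.1.1 lists an extended gap beside death as an exception. This is a fair reading, and it narrows the conflict without removing it. Two adjacent protocol sentences then give different dates for the same death with no stated priority, and 84/168 days still differs from 98.

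**Such deaths will be few.** SAP 2.2 has follow-up only to 35 days after discontinuation and no long-term follow-up. This limits the size, although the schedule of activities (Protocol 1.3.3) continues scans to progression, up to about 24 months, for those who stop treatment for other reasons.

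**Stronger readings that the documents do not support.** From the death sentence alone, a reader might infer that the protocol credits every unscanned death with unlimited progression-free time. It does not: with an inadequate baseline or no adequate scan in 12 weeks, a death after week 12 goes to the start date. Nor is a week-11 death without a scan a conflict, since both documents censor it at death. Nor is the SAP always the stricter document: for an unscanned death on days 85 to 98 it is the more generous one.

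**Conclusion.** The conflict holds for a defined group: adequate baseline, an adequate scan within 12 weeks, then death without documented progression more than 98 days after the last adequate scan. The literal protocol keeps these participants at risk until death; the SAP returns them to the last scan. On the wider reading of *event*, what remains is an unstated priority and unequal gap lengths.

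Where the literal protocol censors later, the effect cannot be unfavourable to lorlatinib. Its size is about 0.3 to 4.7 points on the 12-month estimate for 1 to 8 such deaths in 70. That range rests wholly on the assumed number of deaths, gaps and median; the upper end needs eight deaths, each with a seven-month gap.

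A reader might infer that this threatens the trial's conclusion. It does not: TTP is secondary and descriptive, with no threshold or comparator, and the only decision rule (Protocol 9.2, SAP 5.1.2) concerns the objective response rate. It is a modest point, worth settling before database lock because it is cheap and the possible bias favours the drug.

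**What to change.** Use one gap length for progression and death alike in Protocol 9.4.1 and SAP 6.2.8, for example the SAP's 98 days in place of the protocol's 12 and 24 weeks. State that a progression or death beyond that gap is censored at the last adequate assessment (start date if none), and that this takes priority over the date-of-death rule.

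Inserting 98 days for deaths alone would not do. After week 42, a progression 120 days after the last scan would remain an event while a death after the same gap was pulled back.

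Apply the same length to the rule for participants with no post-baseline scan, so that a death on days 85 to 98 is handled identically in both documents. The protocol repeats its 12/24-week wording for DOR, IC-DOR and PFS, so the chosen length should be carried there too. In the same edit, correct the SAP 6.2.8 bullet that calls an early death a TTP event; Table 4 censors it and the endpoint counts only progression.

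Censoring every death at the last scan is not needed. Both documents use the death date for short gaps, and changing that is a matter of preference.

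The cost is a few lines of text and a slightly less favourable TTP.

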## 1.3.2. Visits on Day 1 of Every Other Cycle (up to 35 cycles and >35 cycles)

Visit Identifier	Visits on Day 1 of Every Other Cycle up to 35 cycles (up to 24 months)	Visits on Day 1 of Every Other Cycle (> 35 cycles or 24 months)	Notes  (X) refer to specific footnote when the measurement may be optional /repeat measurement might not be required.
Visit Window	±4 days	±4 days	
Physical examination	X		
Weight	X		
Contraception check (as	X	X	At cycle not requiring site visit the participant may be contacted by phone to
appropriate)	(every cycle ±2 days)	(every cycle ±2 days)	confirm contraception is still appropriate per the protocol.
Laboratory			

Visit Identifier	Visits on Day 1 of Every Other Cycle up to 35 cycles (up to 24 months)	Visits on Day 1 of Every Other Cycle (> 35 cycles or 24 months)	Notes  (X) refer to specific footnote when the measurement may be optional /repeat measurement might not be required.
Visit Window	±4 days	±4 days	
Pregnancy test	X (every cycle ±2 days)	X (every cycle ±2 days)	Pregnancy tests will be routinely repeated at every cycle (±2 days) during the active treatment period and additionally whenever one menstrual cycle is missed or when potential pregnancy is otherwise suspected. The pregnancy test should be performed at the clinical site's local laboratory. Where that is not possible, participants will provide the laboratory test results carried out at a non-clinical site laboratory, eg, by telephone, and bring a copy of the laboratory test results at the next cycle visit. The copy of the laboratory test results must be retained in the participants' file at the clinical site for documentation purposes.
Study Intervention			
Study Intervention	Once a day continuously		
Tumor Assessments			
CT and MRI Scan or Equivalent	(every 6 weeks ± 1 week)	(As per local clinical practice)	CT and MRI scans to be done at every 6 weeks ±1 week up to approximately 24 months (cycle 35) and then as per local clinical practice.
Other Clinical Assessments			
Adverse Events	X	X	
Concomitant medications and non-drug supportive interventions	X		All concomitant medications and non-drug supportive interventions should be recorded in the CRF until the participant has completed 35 cycles of treatment (approximately 24 months). After cycle 35 the data will be reported in the medical chart, but not collected in the CRF.

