	This analysis is based on ITT population. Participants with an event more than 12 weeks (24 weeks post the first 42 weeks) after the last adequate tumor assessment will be censored on the date of the last adequate tumor assessment prior to the gap that documented no progression. If a new anti-cancer therapy starts prior to an event, the participant will be censored on the date of the last adequate tumor assessment that documented no progression prior to start of the new anti-cancer therapy. Participants with inadequate baseline assessment or with no adequate post-baseline tumor assessments within 12 weeks after the start date will be censored on the start date, unless the participant dies within 12 weeks of the start date, in which case, death will be an event on date of death. The CI for the				
	median PFS will be calculated according to Brookmeyer and Crowley method, and the CIs for the survival function estimates at the timepoints will be derived using the log(-log) method.				

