6.2.5. DoR by ICR/INV

Analysis set: Subsets of Participants with confirmed objective response by ICR/INV

Analysis methodology:

DoR will be calculated on every participant showing OR as follows:

DoR (months) = [first date of PD or death/censoring - first date of CR/PR subsequently confirmed+1]/30.4375

Censoring for DOR will be identical to the censoring rules presented for PFS. Participants with an event more than 14 weeks after the last adequate tumor assessment will be censored on the date of the last adequate tumor assessment prior to the gap that documented no progression. If a new anti-cancer therapy starts prior to an event, the participant will be censored on the date of the last adequate tum or assessment that documented no progression prior to start of the new anti-cancer therapy.

Intercurrent events and missing data: data on response after subsequent anti-cancer therapy is administered will be excluded

Summaries used for reporting: Kaplan-Meier estimates (product-limit estimates) will be presented together with a summary of associated statistics including the median DR time with two-sided 95% CIs. The CIs for the median will be calculated according to Brookmeyer and Crowley.

When the number of participants with PD after a confirmed CR or PR is small, the use of Kaplan-Meier method is limited due to high number of censored observation, so the DOR will be summarized using number (%) of participants with events and of participants censored with DOR in the following categories: less than 6 months, $\geq 6 - <9$, $\geq 9 - <12$, $\geq 12 - <15$, $\geq 15 - <18$, $\geq 18 - <21$, $\geq 21 - <24$, and ≥ 24 months

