6.2.6. IC-DoR by ICR/INV

Analysis set: Subsets of Participants with confirmed Intra-Cranial objective response by ICR/INV

Analysis methodology: IC-DoR (months) = [first date of PD in brain lesions or death/censoring – first date of IC OR (CR/PR subsequently confirmed)+1]/30.4375

For participants whose IC-OR proceeds from PR to CR, the onset of PR is taken as the onset of response.

DMB02-GSOP-RF02 4.0 Statistical Analysis Plan Template 01-Nov-2018 PFIZER CONFIDENTIAL Page 27 TMF Doc ID: 98.03 Censoring for DOR will be identical to the censoring rules presented for PFS.

Intercurrent events and missing data: data on response after subsequent anti-cancer therapy is administered will be excluded.

Summaries used for reporting: The IC-DoR, based on ICR/INV, will be summarized similar to DoR (as described above in section 6.2.5), in Per Protocol Population Participants with CNS metastases based on ICR/INV. Surgery or radiotherapy of extracranial lesions will not affect the determination of IC-OR.

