6.2.7. PFS by ICR/INV

Analysis set: ITT: All enrolled participants who take at least 1 dose of Lorlatinib

Analysis methodology:

PFS is defined as the time from date of first dose to the date of the first documentation of PD per RECIST v1.1 as assessed by ICR/INV or death due to any cause, whichever occurs first and will be summarized in months:

PFS (months) = [date of event or censoring-date of treatment start +1]/30.4375.

PFS data will be censored as follows:

- For participants who start a new anti-cancer therapy prior to an event, censoring will be at the last adequate tumor assessment (see Section 5.2.9) prior to the start of new anti-cancer therapy. Note: if date of progression occurs on the same date as the start of new anti-cancer therapy, the progression will be counted as an event.
- For participants with documented progression or death after two or more missing tumor assessments, censoring will occur at the last adequate tumor assessment prior to the missing assessments. In this study antitumor activity will be assessed through radiological tumor assessments conducted at screening and every 6 weeks until disease progression regardless of initiation of subsequent anti-cancer therapy. The allowable time window for disease assessments is ±1week while on treatment and whenever disease progression is suspected (eg, symptomatic deterioration). Therefore time without adequate assessment is defined as 98 days (12 weeks plus 2 weeks).
- For participants who do not have an adequate baseline tumor assessment or who do not have any post-baseline tumor assessments, censoring will occur on the date of first dose unless death occurred on or before the time of the second planned tumor assessment (ie, on or before day 98) in which case the death will be considered an event. Note for participants who died without any post baseline assessments and meet the definition of two or more missing assessment the reason for censoring will be documented as two or more missed assessments and censoring will occur on the date of first dose.
- All other participants alive without objective progression will be censored on the date of the last adequate tumor assessment.

DMB02-GSOP-RF02 4.0 Statistical Analysis Plan Template 01-Nov-2018 PFIZER CONFIDENTIAL Page 28 TMF Doc ID: 98.03 The date of tumor response at each nominal timepoint based on the ICR/INV assessments will be used for determining the dates of last adequate assessment for censoring purposes.

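### Protocol 9.4.1 and the SAP censor PFS, TTP, DoR and IC-DoR at different assessment gaps, and the protocol's limits do not fit its own 6-weekly scans

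*Protocol*

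**What the plan says.** Protocol 9.4.1 states the gap rule four times, for DoR, IC-DoR, TTP and PFS: an event "more than 12 weeks (24 weeks post the first 42 weeks) after the last adequate tumor assessment" is censored at the last adequate assessment before the gap. For PFS and TTP it adds a 12-week limit for participants with no adequate post-baseline scan. They are censored at the start date unless they die within 12 weeks. Such a death is an event for PFS and is censored on the date of death for TTP.

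The protocol's imaging schedule (1.3.2, repeated in 8.1.1) is "CT and MRI scans to be done at every 6 weeks ±1 week up to approximately 24 months (cycle 35", and local practice applies after that. Nothing changes at week 42.

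The SAP sets one limit. Section 6.2.7 gives its purpose ("For participants with documented progression or death after two or more missing tumor assessments, censoring will occur at the last adequate tumor assessment"), cites the window ("The allowable time window for disease assessments is ±1week while on treatment") and concludes: "Therefore time without adequate assessment is defined as 98 days (12 weeks plus 2 weeks". Section 6.2.8 repeats this for TTP. Section 6.2.5 has "Participants with an event more than 14 weeks after the last adequate tumor assessment will be censored" for DoR, and 6.2.6 says "Censoring for DOR will be identical to the censoring rules presented for PFS". With no post-baseline scan, the SAP's limit for an early death is day 98.

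**The concern.** Both rules are written as operative text for the same endpoints, by ICR and by INV, and they cannot both be programmed. A participant whose progression or death follows a gap of a certain length is an event under one document and censored under the other.

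The protocol's limits also look as if they came from another schedule. A 24-week allowance spans two scan intervals only if scans are 12-weekly, and this study has no 12-weekly phase of CT and MRI scanning.

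At stake are the event counts and medians for PFS, TTP, DoR and IC-DoR, and the 12-month rates for PFS and TTP. These are the durability results of an efficacy study requested by the EMA. The study is open-label and single-arm, so the censoring rule should not be left to be chosen once data have been seen.

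**Working it through.** **Inputs.** Scan interval 42 days and window ±7 days (protocol 1.3.2). Protocol limits 12 × 7 = 84 days and, after week 42, 24 × 7 = 168 days (9.4.1). SAP limit 98 days (6.2.7).

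**The SAP figure reproduces.** Two intervals plus a window at each end: 2 × 42 + 2 × 7 = 98 days.

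**Gap between attended scans after k missed scans**, all within window: (k + 1) × 42 ± 14 days.

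| Missed scans | Shortest | Nominal | Longest |
|---|---|---|---|
| 0 | 28 | 42 | 56 |
| 1 | 70 | 84 | 98 |
| 2 | 112 | 126 | 140 |
| 3 | 154 | 168 | 182 |

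A limit of 98 days separates one missed scan (at most 98) from two (at least 112), which is what the SAP sets out to do.

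**The 24-week branch.** 168 / 42 = 4 intervals. An event at exactly 24 weeks follows three missed scans and still counts.

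**The 12-week branch.** 84 days is two nominal intervals with no window. Suppose both scan dates are uniform over the 15 days of their windows. There are 15 × 15 = 225 pairs, and the gap exceeds 84 days in (225 − 15) / 2 = 105 of them, or 47%. Before the week-42 switch, about half of in-window single-miss gaps therefore lead to censoring.

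**Where the documents disagree.**
- Up to week 42: gaps of 85 to 98 days are censored by the protocol and events in the SAP.
- After week 42: gaps of 99 to 168 days are events in the protocol and censored by the SAP.
- At all times: gaps of 84 days or less, or more than 168 days, are treated alike.
- TTP: only progressions can switch, because deaths are not events under protocol 9.4.1 or SAP Table 4.
- No post-baseline scan: a PFS death at about days 85 to 98 is censored at the start date by the protocol and is an event in the SAP.

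**Size.** The documents give no missed-scan rate, so this part is assumption. A simulation used 15,000 participants per setting, PFS medians of 7 or 12 months, 5% or 15% of scans missed, scan dates uniform within ±7 days, and follow-up of 12 to 24 months. The protocol does not say whether the event or the last scan must fall after week 42, so both readings were run.

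| Week 42 refers to | Event in SAP, censored in protocol | Event in protocol, censored in SAP |
|---|---|---|
| the event | 2.5–7% of PFS events | 0.2–2.0% |
| the last scan | 3–9% | 0.1–0.9% |

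The same settings give 43 to 57 PFS events per 70 participants. The first column is then about 1 participant (0.025 × 43 = 1.1) to 5 (0.09 × 57 = 5.1), and the second at most about 1 (0.02 × 57 = 1.1). Median PFS moved mostly by 0.1 to 0.4 months or by about 1.0 to 1.2 months.

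**The case against.** The strongest reply is that precedence is already settled. Protocol section 9 and the SAP introduction both let the SAP modify the protocol, and an amendment is required only for major changes to the primary endpoint. Protocol 9.4 calls its own text a summary. The four endpoints are secondary, and the SAP derives its limit openly. A programmer would follow the SAP. This largely stands: the SAP rule is the likelier one to be used. It does not cure the protocol text, because the SAP does not declare the change, and its version history ties it to a protocol of 31 Jul 2019 while the one supplied is dated 22 Jan 2020.

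A reader might go further and infer that the protocol governs because the SAP is older. The documents do not support that. The SAP's date is an unfilled placeholder (XX Sep 2019), its front matter is not available here, and neither precedence clause depends on which document is later.

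A reader might also infer that about half of all single-miss events are censored by the protocol. That holds only up to week 42. Later, a single-miss gap of at most 98 days is an event in both documents.

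Nor should the 12-month rates be extended to DoR and IC-DoR. The SAP plans them only for PFS and TTP.

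Finally, the endpoints concerned are descriptive, with no decision rule attached. That is correct and limits the weight of the point.

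**Conclusion.** The conflict is real and follows from the documents alone. The 24-week branch does not fit the protocol's scan schedule. The 12-week branch equals two nominal intervals and fails only by omitting the window.

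The number of participants affected is less certain. It rests on assumed missed-scan rates of 5 to 15%, assumed PFS medians of 7 to 12 months and an unclear week-42 clause. On those terms, roughly 2.5 to 9% of PFS events count only under the SAP and 0.1 to 2% only under the protocol. Median shifts near 1 month should not be read as a loss of information of that size. They partly reflect the Kaplan-Meier median jumping from one 6-weekly scan date to the next.

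The study's success criterion is not affected. The primary ORR uses assessments regardless of gaps, and the decision rule concerns ORR alone. The correction should be made, but it does not threaten the primary conclusion.

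**What to change.** 1. In protocol 9.4.1, use 98 days for DoR, IC-DoR, TTP and PFS, and delete the 24-week clause in all four places.
2. Align the PFS limit for no post-baseline scan to day 98.
3. For TTP, use day 98 as well, but keep early death censored on the date of death. Correct the sentence in SAP 6.2.8 that makes such a death an event, so that it agrees with SAP Table 4 and protocol 9.4.1. Copying the SAP's day-98 text into TTP unchanged would import that error.
4. In SAP 2.1.2, remove the statement in the DoR and IC-DoR estimands that gaps are disregarded. It contradicts the 14-week rule in 6.2.5 and 6.2.6.
5. Update the SAP version history to the current protocol and list the change there.

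Letting the gap rule simply lapse at month 24, when scans pass to local practice, is not a solution: with nothing in its place, an event after any later gap would count.

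The cost is wording in two documents. No new data or assessments are needed.
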